5.0 Study Procedures

5.1 Study Design

This study will consist of two parts. Part 1 is diagnostic in nature, whereas Part 2 is a preliminary treatment study that will include a portion of the participants from Part 1.

Part 1 Procedures

The participants completing this study will be veterans between the ages of 20 and 50 years and divided into 4 groups: 2 groups of 117 veterans who report histories of blast exposure and blast-related clinical signs consistent with the VA/DoD definition of mTBI (VA/DoD, 2009) and present with normal or near normal results on standard audiometric testing but who report substantive problems with audition; a group of 117 normal hearing controls who report no auditory problems and no histories of blast exposure, brain injury, or psychiatric disorder (Normal Controls); and a group of 117 normal hearing veterans with PTSD and no blast exposure or blast-related clinical signs (PTSD-only). Of the two groups of veterans with auditory complaints one group will present with little or no PTSD (mTBI-only), whereas the other group will be symptomatic for PTSD (mTBI+PTSD). A total of 468 participants will complete the study and 50 additional participants will be allowed for experimental attrition.

In addition to the 468 veteran participants, 468 family members or friends (significant others) will complete a questionnaire about the veterans' hearing handicap.

After a telephone screen and preliminary testing, a battery of behavioral and physiological measures will be administered to all 4 groups of veterans to characterize the level and nature of their auditory impairments. Included are tests and procedures that likely will capture underlying or related problems and are commonly used in clinical and experimental studies of the peripheral auditory system, central auditory processing disorders, speech and language perception in noise, and executive function in persons with brain injury.

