All these participants (including normal controls) will be recruited using the following procedures. They will be recruited through flyers distributed in various clinics (e.g., audiology, behavioral health, neuropsychology) at the three participating VA sites. In addition, participants will be recruited through research registries at the study sites and national VA and military research registries, such as the Corporate Data Warehouse through Data Access Request Tracker (DART) via the VA Data Portal/VINCI and the VA database for individuals who have initial positive TBI screens (<https://vssc.med.va.gov/tbireports/TBI.aspx>). The study will adhere to contact methods approved by the individual registries. Flyers and list serve announcements will be provided to veteran organizations/offices at the university affiliates of the participating sites for distribution (flyer and announcement attached). Flyers and list serve announcements also will be provided to local veteran organizations for distribution. Clinical audiologists at the three sites will be informed of the study and if they so choose, can provide potential participants with flyers so that the potential participants can contact study personnel to learn more about the study. Research staff members

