5.6 Data Analysis

Part 1 Analysis

Preliminary Analyses - The analysis will begin with basic descriptive statistics including means and standard deviations for continuous data and examination of distributional assumptions for all study measurements including the questionnaire data (e.g., HHIA, WHODAS-II, SSQ and HHIA-SO) for each group of interest. These analyses will be used to evaluate the extent of missing data and to identify outliers.

Primary Analyses - Random Forests (RF, Breiman, 2001) will be applied to determine which auditory, language processing, and executive function variables best discriminate the three groups. This technique performs variable selection and the variables are ranked by Gini score, a measurement of average accuracy of all trees containing a particular variable. One-way ANOVA will be used to determine differences between groups for normally distributed continuous data. Analysis of covariance (ANCOVA) will be used to adjust for differences between groups. If assumptions for the parametric test are not met, a non-parametric alternative will be used (e.g., Kruskal-Wallis, non-parametric ANCOVA). The p-values will be adjusted for multiple testing by using a false discovery rate method whenever more than one variable is being tested. Statistical assumptions (e.g., linearity, normality) will be verified prior to hypothesis testing. All statistical analyses will be two sided and the significance level will be 0.05.

Sample Size and Power - A sample size of 117 per veteran group will achieve 80% power at a 0.05 significant level to detect an effect size (i.e., odds ratio) of 2.50. This sample size was computed based on an adjustment that was made assuming that a multiple regression of the independent variable of interest on the other independent

variables in the model will result in an R-squared of 0.20. For one-way ANOVA, the total sample of 468 subjects achieves 80% power to detect an effect size of 0.18 or larger with a two-sided significance of 0.01 to account for multiple hypotheses testing. For analysis of covariance, the study is powered (0.80) to detect an effect size of 0.16 assuming the strength of the relationship between the response of interest and the covariates, measured as R-squared, is 0.20.

Part 2 Analysis

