Primary Analyses – Basic descriptive statistics will be computed and examination of statistical assumptions will be performed for all study measurements. For questionnaire data, analysis of variance (ANOVA) or Kruskal Wallis test will be used to determine differences in the overall and subset scores between the mTBI groups. The analysis will also include basic descriptive statistics for behavioral data test measures at baseline and at 6 months for the mTBI-only and mTBI+PTSD groups, and at baseline and 12 months for the delayed-treatment groups. We will focus on the changes in the behavioral test measures from baseline to 6 months (mTBI-only and mTBI+PTSD treatment groups) and from baseline to 12 months (delayed-treatment groups). Specifically, paired t-test or Wilcoxon signed rank test will be used to determine change at 6 or 12 months and this test will be applied to each behavioral test measure separately. False discovery rate will be used to adjust the p-values for multiple hypotheses testing. All statistical analyses will be two sided and the significance level will be 0.05.

Secondary Analyses – For longitudinal analysis, the data will be modeled using linear-mixed models for which the outcome is the behavioral test measure across time. The predictors will include time, group and interaction between group and time. Covariates will be added to the model as needed. In addition, variables with a high Gini score from Part 1 will be correlated with final hearing aid results as a preliminary investigation of whether hearing aid benefit can be associated by any of the variables obtained above. We will measure correlations using either Pearson's or Spearman's correlation coefficient. We will adjust the p-values for multiple testing by using a false discovery rate method whenever more than one variable is being tested. Single-subject design metric also will be used to investigate individual responses to the hearing aid treatment.

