8.0 Communication Plan

The PI and lead investigators will have conference calls at least twice per month to maintain coordination of the study activities and to address any issues. Once a year, the PI will meet face-to-face with Drs. [name] and [name] and their respective study teams to check procedural fidelity and data integrity. Additional meetings will be scheduled as needed.

Data monitoring will occur monthly by the lead investigator at each sites with monthly reports submitted to the PI for review and signature. The participant safety and data accrual, security, and fidelity will be reviewed by site and in aggregate. In addition, all three teams will complete yearly internal audits to confirm the fidelity of their procedures and documentation, and to insure appropriate data quality and security. The results of these audits also will be reviewed by the PI with corrective actions taken and reported as needed. The data accrual is expected to be 50% at the Pittsburgh site, 25% at the PVAMC site and 25% at the VASFHS/University of South Dakota site. If more than 5%

of participants per year per site have protocol deviations, the study personnel at that site will receive re-training. The lead investigators at each site will receive copies of the documents approved by the Central IRB for the study, and the documents required for submission at the local site.

To ensure that all regulatory and IRB requirements have been met at each site prior to implementing the study procedures, the lead investigators at each site will submit a copy of the local IRB application, consent forms, HIPAA documents and approval letters to the PI.

Copies of all Central and local IRB documents will be retained in regulatory binders by the PI and the lead investigators at each site will retain copies of the Central IRB documents transmitted to them, as well as their local IRB documents.

Serious Adverse Events and Unanticipated Problems will be reported to the lead investigator at each site who will contact the PI. Documentation will be submitted to the Central IRB by the lead investigator with copies submitted to the PI. Copies of the reports will be retained by the PI and the lead investigator at their site. The PI also will submit interim results that may impact conduct of the study.

All sites will continue to collect data until the full complement of participants has completed the study or until the study has been concluded.

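### Part 1 compares four recruited groups across three sites, but site is not pre-specified in the one-way ANOVA, the ANCOVA or the mixed model

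*Combined protocol and SAP*

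**What the plan says.** Section 5.2 recruits through clinics "at the three participating VA sites", and through registries, university affiliates, local veteran organisations and record review. Section 8.0 states: "The data accrual is expected to be 50% at the Pittsburgh site, 25% at the PVAMC site", and puts the remaining 25% at the third site. This is a split of all participants; it is not broken down by group.

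Section 5.1 sets four groups of 117: "A total of 468 participants will complete the study and 50 additional participants will be allowed for experimental attrition". Membership follows from blast history and screening results, so Part 1 has no random allocation.

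For the Part 1 group comparisons, section 5.6 states: "One-way ANOVA will be used to determine differences between groups for normally distributed continuous data". The next sentence adds: "Analysis of covariance (ANCOVA) will be used to adjust for differences between groups". Its covariates are not named. Non-parametric alternatives are allowed, and p-values are adjusted by a false discovery rate method.

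For the Part 2 mixed model, section 5.6 states: "The predictors will include time, group and interaction between group and time". It then leaves further covariates open, to be added where necessary.

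Site is not listed as a factor, covariate, random effect or stratification variable in either part. No group target by site appears in the text available, which does not include sections 1.0 and 4.0.

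**The concern.** When groups are recruited at several sites, nothing in the design forces the same mix of groups at each site. Local clinics, registries and record reviews could easily yield more blast-exposed veterans at one site and more controls at another. The battery includes evoked potentials, otoacoustic emissions, tuning curves and other laboratory measures. For these, a level difference between laboratories is possible even with common procedures.

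If both conditions occur, a group-only ANOVA attributes part of the site difference to group. The false discovery rate method takes the p-values as given. It controls multiplicity among valid p-values and does not repair p-values whose null distribution has been shifted by confounding. Because many outcomes are tested, a covariate set left open until the data are seen also leaves room for choice outcome by outcome.

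**Working it through.** **1. The plan's own figure.** Section 5.6 states that "the total sample of 468 subjects achieves 80% power to detect an effect size of 0.18 or larger with a two-sided significance of 0.01". For one-way ANOVA with k = 4 and N = 468, the degrees of freedom are 3 and 464 and the noncentrality is λ = N·f². At f = 0.18, λ = 468 × 0.0324 = 15.16. With the 0.01 critical value F = 3.82, power is 0.783, and 80% power is reached at f = 0.183. The stated figure reproduces to rounding.

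**2. Cost of a site term when groups are balanced over sites.** Error degrees of freedom fall from 464 to 462. Power at f = 0.18 stays 0.783 and the detectable f stays 0.183.

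**3. Effect of leaving site out.** Assume no true group difference, within-site SD of 1, and a shift of δ at Pittsburgh relative to the other two sites. Let p_g be the share of group g tested at Pittsburgh. Then:

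- expected group mean: m_g = p_g·δ
- spurious difference between two groups: (p_g − p_h)·δ
- within-group variance: w = 1 + δ²·average of p_g(1 − p_g)
- noncentrality: λ = 117·Σ(m_g − m̄)² / w

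The inputs p_g and δ are assumptions. The mixes used average 50% at Pittsburgh, as section 8.0 expects. If every p_g equals 0.5, all m_g are equal, λ = 0, and the test holds its level for any δ.

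Worked case: shares 65/65/35/35% (both blast groups against the other two) and δ = 0.5. The means are 0.325, 0.325, 0.175 and 0.175, each 0.075 from their average. So Σ(m_g − m̄)² = 4 × 0.005625 = 0.0225; w = 1 + 0.25 × 0.2275 = 1.057; λ = 117 × 0.0225 / 1.057 = 2.49.

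| Pittsburgh share, blast v other groups | δ (SD) | Spurious difference (SD) | λ | Rejection at 0.05 | Rejection at 0.01 |
|---|---|---|---|---|---|
| 50 v 50 | any | 0 | 0 | 0.050 | 0.010 |
| 60 v 40 | 0.25 | 0.05 | 0.29 | 0.067 | 0.015 |
| 60 v 40 | 0.5 | 0.10 | 1.10 | 0.123 | 0.036 |
| 65 v 35 | 0.25 | 0.075 | 0.65 | 0.091 | 0.023 |
| 65 v 35 | 0.5 | 0.15 | 2.49 | 0.231 | 0.086 |

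In simulations under the same kind of assumptions (4,000 datasets per setting), adding site brought rejection back to 4.5% to 5.4% at nominal 0.05 and 0.8% to 1.1% at nominal 0.01.

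**4. Cost of a site term when groups are not balanced.** Site is then partly collinear with group. The squared correlation of the Pittsburgh indicator with group is Var(p_g)/0.25, and the variance of the contrast aligned with the imbalance rises by 1/(1 − R²).

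- 60/40: R² = 0.01/0.25 = 0.04, inflation 1.04, λ = 15.16/1.04 = 14.56, power at f = 0.18 is 0.76.
- 65/35: R² = 0.0225/0.25 = 0.09, inflation 1.10, λ = 13.80, power 0.73.
- 70/30: R² = 0.04/0.25 = 0.16, inflation 1.19, λ = 12.74, power 0.68.

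These are worst-direction values.

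**5. Part 2.** A constant site shift enters a person's baseline and follow-up equally, so it cancels in the paired tests and in the group-by-time term. Only a site-by-time difference would disturb those. Treatment and delayed treatment are randomly assigned within each mTBI group (section 5.2), so no systematic site imbalance is expected there. What remains exposed is mainly the group main effect for mTBI-only against mTBI+PTSD, which is not randomised.

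**The case against.** The best counter-argument is that the plan does not exclude site. The ANCOVA is there to handle differences between groups, it is powered with a covariate R-squared of 0.20, and the mixed model leaves covariates open. A reader might infer from the ANOVA sentence and the listed mixed-model predictors that site adjustment is ruled out. The sentences that follow them do not support that. The defect is that site is not named in advance.

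A reader might also take the 50/25/25 split as the imbalance itself. It is not: with equal group shares at each site there is no inflation at all. The documents report neither a group-by-site mix nor a site effect. Section 5.2 applies the same recruitment procedures to all groups, controls included. Section 5.1 has most tests given in the standard manner, and section 8.0 provides yearly fidelity visits, audits and re-training. These make large site shifts less likely, though they are conduct controls and do not adjust an analysis.

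Size also counts. Spurious differences of 0.05 to 0.15 SD are well below the 0.36 SD (2 × 0.18) that f = 0.18 represents when two groups are set against two. The 23% rejection rate is the most extreme of the settings shown.

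All of this stands as a limit on the claim. It does not remove the case for naming a recorded three-level factor in advance.

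**Conclusion.** The point holds as a gap in pre-specification with a foreseeable consequence. It is not a demonstrated bias. If the group mix differs by site and sites differ on the outcome by 0.25 to 0.5 SD, the unadjusted Part 1 ANOVA would reject a true null about 7% to 12% of the time at 60/40 and 9% to 23% at 65/35, against a nominal 5%. At the 0.01 level used in the plan's power statement, the range over these settings is about 1.5% to 9%. The site mixes and shifts are both assumptions.

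It would be tempting to conclude that the Part 2 treatment findings are confounded by site as well. The documents do not support that: the paired tests and group-by-time term cancel a constant site shift, and treatment against delayed treatment is randomly assigned. The concern is mainly about Part 1.

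**What to change.** In section 5.6, pre-specify site (three levels) as a fixed factor in every Part 1 ANOVA and ANCOVA, and carry it into the non-parametric alternative, for example as a term in the non-parametric ANCOVA already allowed. Report group-by-site counts with the descriptive statistics, so that readers can see how far group and site overlap. Add site to the Part 2 mixed model, noting that it bears mainly on the mTBI-only against mTBI+PTSD main effect.

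The cost is a change of wording and 2 degrees of freedom, with negligible loss of power if groups are balanced over sites. If they are not, power at f = 0.18 in the worst-case direction falls from about 0.78 to about 0.76 at 60/40 or 0.68 at 70/30. That loss arises only when the mix is uneven, which is also when the unadjusted comparison is open to site bias.
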